### 10.62 Submit via appropriate MCCC Case Report Forms (i.e., paper or electronic, as applicable) the following AEs experienced by a patient and not specified in Section 10.6:

10.621 Grade 2 AEs deemed *possibly, probably, or definitely* related to the study treatment or procedure.

10.622 Grade 3 and 4 AEs regardless of attribution to the study treatment or procedure.

10.623 Grade 5 AEs (Deaths)

10.6231 Any death within 30 days of the patient's last study treatment or procedure regardless of attribution to the study treatment or procedure.

10.6232 Any death more than 30 days after the patient's last study treatment or procedure that is felt to be at least possibly treatment related must also be submitted as a Grade 5 AE, with a CTCAE type and attribution assigned.

## 10.7 Late Occurring Adverse Events

Refer to the instructions in the Forms Packet (or electronic data entry screens, as applicable) regarding the submission of late occurring AEs following completion of the Active Monitoring Phase (i.e., compliance with Test Schedule in Section 4.0).

## 10.8 Adverse Events of Special Interest (AESI)

Specific adverse events, or groups of adverse events, will be followed as part of standard safety monitoring activities. These events (regardless of seriousness) will be reported to Pharmacyclics Drug Safety per SAE reporting timelines.

### 10.8.1 Major Hemorrhage

Major hemorrhage is defined as any of the following:

- Any treatment-emergent hemorrhagic adverse events of Grade 3 or higher\*. Any treatment-emergent serious adverse events of bleeding of any grade
- Any treatment-emergent central nervous system hemorrhage/hematoma of any grade

\*All hemorrhagic events requiring transfusion of red blood cells should be reported as grade 3 or higher AE per CTCAE v4.0.

Events meeting the definition of major hemorrhage will be captured as an event of special interest according to Section 10.8 above.

## 11.0 Treatment Evaluation - The International Myeloma Working Group (IMWG) uniform response criteria (Kumar et al, 2016) will be used to assess response to therapy

### 11.1 Terms and definitions

- **M-protein:** synonyms include M-spike, monoclonal protein and myeloma protein, paraprotein, M-component.

Serum M-protein level is quantitated using densitometry on SPEP except in cases where the SPEP is felt to be unreliable.

- M-proteins migrating in the β-region (usually IgA M-proteins)
- Cases in which the M-protein is so large and narrow on agarose (some specimens >4 g/dL) that they underestimate the actual immunoglobulin level (by greater than 1500 mg/dL) due to technical staining properties of the agarose gel.
- Cases in which there are multiple peaks of same M-protein (aggregates or dimers)

If SPEP is not available or felt to be unreliable (above examples) for routine M-protein quantitation, then quantitative immunoglobulin levels derived from nephelometry or turbidometry can be accepted, with the exception that quantitative IgG may not be used. However, this must be explicitly reported at baseline, and only nephelometry can be used for that patient to assess response. SPEP derived M-protein values and quantitative nephelometric immunoglobulin values cannot be used interchangeably.

Urine M-protein measurement is estimated using 24-h UPEP only. Random or 24 h urine tests measuring kappa and lambda light chain levels are not

reliable and are not recommended.

**FLC estimation** is currently carried out using the serum FLC assay (Freelite, The Binding Site Limited, UK). Patients with kappa/lambda FLC ratio  $<0.26$  are defined as having monoclonal lambda FLC and those with ratios  $>1.65$  as having a monoclonal kappa FLC. The monoclonal light chain isotype is considered the involved FLC isotype, and the opposite light chain type as the uninvolved FLC type.

- **Response terms:** The following response terms will be used: stringent Complete Response (sCR), complete response (CR), very good partial response (VGPR), partial response (PR), Minimal Response (MR), stable disease (SD), and progressive disease (PD).

In addition, for each response category, there will be an “unconfirmed” response category, which will be for internal use, for the purpose of guiding decision making and test ordering. These designations will be applied at the time of the first measurement at which the quantitative aspect of the response category has been satisfied without the confirmation step having been satisfied. The designation “u” will precede the standard abbreviations, and will include usCR, uCR, uVGPR, uPR, uMR, uPD.

- **Measurable disease:** Patients who have a measurable serum or urine M-protein.
  - Serum M-protein  $\geq 1$  g/dl  
NOTE: Quantitative IgG may not be used for defining measurable disease
  - Urine M-protein  $\geq 200$  mg/24 h
  - Serum FLC assay: Involved FLC level  $\geq 10$  mg/dl provided serum FLC ratio is abnormal
  - Bone marrow plasma cells  $\geq 30\%$

The serum free light chain (FLC) assay is of particular use in monitoring response to therapy in patients who have oligo-secretory or non-secretory disease and **should be used in assessing response only if the baseline serum and/or urine M proteins are not “measurable” as above, and the baseline level of the involved FLC is “measurable.”** When using this assay, it is important to note that the FLC levels vary considerably with changes in renal function and in patients with renal insufficiency, the levels of both the kappa and lambda may remain elevated, but the ratio normalizes with achievement of CR. Thus, both the level of the involved and the uninvolved FLC isotype (i.e., the involved/uninvolved ratio or involved-uninvolved difference) should be considered in assessing response. ***Patients included on the study on the basis of FLC alone (i.e., no measurable serum/urine M-protein) should be the only ones who are evaluated using FLC response criteria. The others should follow usual criteria and ignore FLC results*** with the exception of defining stringent complete

response.

- **Evaluable disease**: Patients who do not have a “measurable” serum M-protein, serum free light chain, or urine M-protein.
- **Oligosecretory myeloma**: Patient with multiple myeloma who has NEVER had “measurable” serum M-protein or urine M-protein, but has had a detectable M-protein in his/her serum and/or urine and/or measurable serum free light chain.
- **Non-secretory myeloma**: Patient with multiple myeloma who has NEVER had a detectable M-protein in his/her serum and/or urine.

## 11.2 Clarification of test indications

Listed below are the minimal required tests required to assess response based on the characteristics of their disease at on study.

Table 11.2				
Tests Required To Assess Response (Must Be Done At Each Disease Measurement Visit except as indicated  )				
On Study Baseline Value	SPEP 	24 hr UPEP 	Ig FLC	BM Bx
Serum M-protein $\geq$ 1 g/dl, and urine M-protein $\geq$ 200 mg/24 hrs	X	X		
Serum M-protein $\geq$ 1 g/dl, but urine M-protein < 200 mg/24 hrs	X			
Serum M-protein <1 g/dl, and urine M-protein $\geq$ 200 mg/24 hrs		X		
Serum M-protein < 1 g/dl, urine M-protein < 200 mg/24 hrs, but involved Ig FLC is $\geq$ 10 mg/dL			X	
Serum M-protein < 1 g/dl, urine M-protein < 200 mg/24 hrs, involved Ig FLC is <10 mg/dL, bone marrow $\geq$ 30% plasma cells				X 

 ***SPEP, UPEP, Immunofixation studies of both serum and urine, and Bone marrow biopsy*** are required to document CR regardless of registration values, and in addition ***FLC measurement and bone marrow immunophenotyping*** is required to document sCR. SPEP and UPEP are required to document VGPR regardless of registration values.

 For serum measurable patients, 24 hour urine does not need to be confirmed (i.e. repeated after documented response) for any response category

 At a minimum, a bone marrow biopsy should be repeated every 3 months until documented response. Bone marrow biopsy results do not need to be repeated after documented response.

 If serum M-protein is being followed by quantitative immunoglobulin levels derived from nephelometry or turbidometry, quantitative immunoglobulins are required. SPEP is only required to document CR or VGPR.

### 11.3 Confirmed response

In order to be classified as a hematologic response, confirmation of serum M-protein, serum immunoglobulin free light chain (when primary determinant of response) and urine M- protein (when primary determinant of response) results must be made by verification on two consecutive determinations.

- Bone marrow aspirate and biopsy are **only** required to document CR or sCR, except for patients with evaluable disease **only**, where a bone marrow is required to document all response categories including progression. However, a second confirmatory bone marrow is **not** required to confirm response in any case.
- Radiographic studies are not required to satisfy these response requirements; however, if radiographic studies were performed there should be no evidence of progressive or new bone lesions.

Appropriate tests required to document and confirm response are listed in Table 11.2

### 11.4 Bone progression

Caution must be exercised to avoid rating progression on the basis of variation of radiologic technique alone. Compression fracture does not exclude continued response and may not indicate progression. When progression is based on skeletal disease alone, it should be discussed with the Study Chair before removing the patient from the study.

### 11.5 Response and Progression

Criteria for response and progression are listed in Table 11.5. Progressive disease for all patients as defined in Table 11.5.

Baseline values for disease assessment: All disease response measurements will be based on the values obtained at the time of diagnosis if there has been no relapse prior to transplant. If patients had a disease relapse prior to transplant, the baseline values will be those obtained at the time of relapse immediately prior to the transplant. If patient had treatment for the relapsed disease prior to transplant, the values will be from prior to this therapy, ie, the time of relapse.

Table 11.5

IMWG MRD NEGATIVITY CATEGORY	RESPONSE CRITERIA a
Flow MRD k	Absence of phenotypically aberrant clonal plasma cells by MPF on bone marrow aspirates using the EuroFlow standard operation procedure for MRD detection in multiple myeloma (or validated equivalent method) with a minimum sensitivity of 1 in $10^5$ nucleated cells or higher
Imaging + MRD-negative	MRD negative as defined by MPF or NGS PLUS Disappearance of every area of increased tracer uptake found at baseline or a preceding PET/CT or decrease to < mediastinal blood pool Standard uptake value or decrease to less than that of surrounding normal tissue
STANDARD IMWG RESPONSE CATEGORY	RESPONSE CRITERIA a
Stringent Complete Response (sCR) b	CR as defined plus Normal FLC ratio and • Absence of clonal PCs by immunohistochemistry or 2- to 4-color flow cytometry i
Complete Response (CR) b	• Negative immunofixation of serum and urine c and • Disappearance of any soft tissue plasmacytoma and • <5% PCs in Bone Marrow and • If the only measurable disease is FLC, a normal FLC ratio d
Very Good Partial Response (VGPR)	• Serum and urine M-protein detectable by immunofixation but not on electrophoresis c or • $\geq 90\%$ reduction in serum M-protein and urine M-protein <100 mg/24 h c • If the only measurable disease is FLC, a $>90\%$ reduction in the difference between involved and uninvolved FLC levels
Partial Response (PR)	• If present at baseline, $\geq 50\%$ reduction of serum M-protein and reduction in 24-hour urinary M-protein by $\geq 90\%$ or to <200 mg/24hrs c • If the only measurable disease is FLC, a $\geq 50\%$ reduction in the difference between involved and uninvolved FLC levels • If the only measurable disease is BM, a $\geq 50\%$ reduction in BM PCs (provided the baseline PCs was $\geq 30\%$ ) • If present at baseline, $\geq 50\%$ reduction in the size (SPD) of soft tissue plasmacytomas j
Minor Response (MR)	• If present at baseline, $\geq 25\%$ but $\leq 49\%$ reduction of serum M protein and reduction in 24-hour urine M-protein by 50-89% which still exceeds 200mg/24 hours c and • If present at baseline, $\geq 50\%$ reduction in the size (SPD) of soft tissue plasmacytoma j

Stable Disease (SD)	
 
Not meeting criteria for sCR, CR, VGPR, PR, MR or PD
 

Progressive Disease (PD) b, h	
Increase of 25% from lowest value in any of the followingf, g:
 
 
Serum M-protein (absolute increase must be <math>\geq 0.5</math> g/dL) and/or
 
Urine M-protein (absolute increase must be <math>\geq 200</math> mg/24 hrs) and/or
 
If the only measurable disease is FLC, the difference between involved and unininvolved FLC levels (absolute increase must be <math>>10</math> mg/dL) and/or
 
If the only measurable disease is BM, bone marrow PC percentage (absolute increase must be <math>\geq 10\%</math>)e
 
 
Or any one or more of the following:
 
 
Development of new bone lesion or soft tissue plasmacytoma or <math>\geq 50\%</math> increase from nadir in the size (SPD) of existing bone lesions or soft tissue plasmacytoma or <math>\geq 50\%</math> increase in the longest diameter of a previous lesion <math>>1</math> cm in short axisj
 
50% increase in circulating plasma cells (minimum of 200 cells per L) if this is the only measure of disease
 

Clinical Relapse	
One or more of the following direct indicators of increasing disease and/or end-organ dysfunction that are considered related to the underlying plasma cell proliferative disorder:
 
 
Development of new soft tissue plasmacytomas or bone lesions on skeletal survey, magnetic resonance imaging, or other imaging
 
Definite increase in the size of existing plasmacytomas or bone lesions. A definite increase is defined as a 50% (and at least 1 cm) increase as measured serially by the sum of the products of the cross-diameters of the measurable lesion
 
Hypercalcemia (<math>>11.5</math> mg/dL; <math>>2.875</math> mM/L)
 
Decrease in hemoglobin of more than 2 g/dL (1.25mM) or to less than 10 g/dL
 
Rise in serum creatinine by more than or equal to 2 mg/dL (<math>\geq 177</math> mM/L)
 
Hyperviscosity
 

a All response categories require two consecutive assessments (sCR, CR, VGPR, PR, MR, PD) made at any time before the institution of any new therapy. MRD tests should be done as specified per the test schedule. sCR, CR, VGPR, PR, MR and SD categories and MRD require no known evidence of progressive or new bone lesions or extramedullary plasmacytomas if radiographic studies were performed. However, radiographic studies are not required to satisfy these response requirements. Bone marrow assessments need not be confirmed. Each category, except for stable disease, will have a working subcategory of “unconfirmed” [prefix ‘u’] to designate first time point at which response category MAY have been achieved if confirmed. The date of the initial test is considered as the date of response for evaluation of time dependent outcomes such as duration of response.

b CR patient will need to progress at the same level as VGPR and PR patients to be considered a PD. A positive immunofixation alone is not sufficient. If a patient has already achieved a complete response prior to registration as a result of the induction therapy, the patient will be considered a continued complete response if they continue to meet the complete response criteria at the next assessment. Reconfirmation of complete response is not required.

c If more than one M protein spike meets the criteria for measurable disease at baseline, then both need to be followed for response. Otherwise, only follow the measurable M protein spike for response.

d In patients in whom the only measurable disease is by serum FLC levels: CR in such patients indicates a normal FLC ratio of 0.26-1.65 in addition to the CR criteria listed above.

e Bone marrow criteria for PD are only to be used in patients without measurable disease by M protein and by FLC;

f A "25% increase" refers to M protein, FLC and bone marrow results and does not refer to bone lesions, soft tissue plasmacytoma or hypercalcemia. The lowest value does not need to be a confirmed value. If the lowest serum M-protein is  $\geq 5$  g/dL, an increase in serum M-protein of  $\geq 1$  g/dL is sufficient to define disease progression.

g In the case where a value is felt to be a spurious result per physician discretion (for example, a possible lab error), that value will not be considered when determining the lowest value.

h Progressive disease should be confirmed on two consecutive evaluations, where the timing of confirmation is per the treating physician and can be done immediately within the same cycle or on the next cycle. However, treatment may be discontinued for progressive disease that is unconfirmed per physician discretion. In this case, an objective status of PD should be entered on the measurement form and progressive disease should be reported on the event monitoring form.

i Presence/absence of clonal cells is based upon the k/l ratio. An abnormal k/l ratio by immunohistochemistry requires a minimum of 100 plasma cells for analysis. An abnormal ratio reflecting presence of an abnormal clone is k/l of 4:1 or 1:2.

j Plasmacytoma measurements should be taken from the CT portion of the PET/CT, or MRI scans, or dedicated CT scans where applicable. For patients with only skin involvement, skin lesions should be measured with a ruler. Measurement of tumor size will be determined by the sum of the products of the maximal perpendicular diameters of measured lesions (SPD).

k Requires a complete response as defined in the table. MRD tests should be done as specified per the test schedule. MRD requires no known evidence of progressive or new bone lesions if radiographic studies were performed. However, radiographic studies are not required to satisfy these response requirements. **NOTE: An objective status of MRD negative should be reported on the treatment measurements form only when flow MRD by bone marrow is negative.**

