### 1.3 Role of Daratumumab in Multiple Myeloma

Daratumumab is an immunoglobulin G1 kappa (IgG1k) human monoclonal antibody (mAb) that binds to a unique CD38 epitope on CD38-expressing cells with high affinity. It was developed by the immunization of human immunoglobulin transgenic mice with recombinant CD38 protein. CD38 is a 46-kDa type II transmembrane glycoprotein that is highly expressed on MM cells. CD38 has various mechanisms including ectoenzymatic activity, receptor-mediated regulation of cell adhesion and signal transduction. Preclinical studies have shown that daratumumab induces MM cell death through several mechanisms, including complement-dependent cytotoxicity (CDC), antibody-dependent cell-mediated cytotoxicity (ADCC), antibody-dependent cellular phagocytosis (ADCP), and FcR mediated-crosslinking inducing apoptosis. In a combined analysis of GEN501 and SIRIUS studies including 148 patients, the Overall Response Rate (ORR) was 31 %, and at a median follow-up of 14.8 months, the estimated Overall Survival (OS) was 19.9 months. These trials demonstrated that daratumumab is active as monotherapy in patients with heavily pre-treated and relapsed/refractory myeloma (RRMM) alongside maintaining its anti-myeloma activity in previously treatment refractory patients as evident by ORR 33 and 29.7 % in GEN501 and SIRIUS, respectively. Preclinical studies have shown that Daratumumab in combination with other agents enhances the antimyeloma activity and now there are reported multiple phase II /III trials to study the same. These include data from the CASTOR and POLLUX trials of the combination of daratumumab and dexamethasone with bortezomib and lenalidomide, respectively, showing enhanced efficacy of these regimens in patients with early relapsed MM (2nd or 3rd line) and low minimal residual disease (MRD) states leading to the FDA approval of these regimens.

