Following the administration of the recommended dose of 1,800 mg daratumumab and 30,000 units hyaluronidase subcutaneously once weekly for 8 weeks, the mean  $\pm$  standard deviation (SD) maximum trough concentrations ( $C_{\text{trough}}$  following the 8th dose) were  $593 \pm 306 \mu\text{g/mL}$  compared to  $522 \pm 226 \mu\text{g/mL}$  for daratumumab 16 mg/kg administered intravenously, with a geometric mean ratio of 108% (90% CI: 96, 122). The estimated median daratumumab area under the concentration-time curves (AUC0-7 days) and daratumumab peak concentration ( $C_{\text{max}}$ ) following the 8th dose were comparable between subcutaneous and intravenous daratumumab ( $4017 \mu\text{g/mL}\cdot\text{day}$  vs.  $4,019 \mu\text{g/mL}\cdot\text{day}$  for AUC0-7 days and  $592 \mu\text{g/mL}$  vs.  $688 \mu\text{g/mL}$  for  $C_{\text{max}}$ ). The absolute bioavailability of daratumumab-hyaluronidase is 69%, with peak concentrations occurring around 3 days ( $T_{\text{max}}$ ). The estimated mean (coefficient of variation, CV) volume of distribution for the central compartment is 5.2 L (37%) and peripheral compartment was 3.8 L with the daratumumab-hyaluronidase formulation. Daratumumab is cleared by parallel linear and nonlinear saturable target mediated clearances. The estimated mean (CV%) linear clearance of daratumumab is 119 mL/day. The estimated mean (CV%) elimination half-life associated with linear clearance is 20 days (22%).

**Body Weight (BW):** After administration of 1,800 mg daratumumab and 30,000 units hyaluronidase subcutaneously once weekly for 8 weeks, the mean maximum  $C_{\text{trough}}$  was 12% lower in the higher body weight group ( $>85 \text{ kg}$ ) while the mean maximum  $C_{\text{trough}}$  was 81% higher in the lower BW group ( $\leq 50 \text{ kg}$ ) compared to the corresponding BW groups in the intravenous daratumumab arm.

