#### 16.41 Primary Outcome Analysis:

16.411 Definition: The primary endpoint of this trial is the rate of MRD negative response after ASCT. MRD negative response after ASCT is defined as achievement of MRD negative status in the bone marrow by flow cytometry (MPF) at the day 100 post ASCT visit. All patients meeting the eligibility criteria who have signed a consent form and have begun treatment will be evaluable for response, unless they are determined to be a major violation.

16.412 Estimation: The proportion of successes will be estimated by the number of successes divided by the total number of evaluable patients. Ninety-five percent confidence intervals for the true success proportion will be calculated according to the approach of Duffy and Santner.

16.413 Over Accrual: If more than the target number of patients are accrued, the additional patients will not be used to evaluate the stopping rule or used in any decision making processes; however, they will be included in final point estimates and confidence intervals

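### CR requires negative serum immunofixation, but Section 11 has no rule for a band produced by daratumumab, itself a monoclonal IgG kappa present in serum at the on-treatment visits

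*Combined protocol and SAP*

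**What the plan says.** In Table 11.5 the first condition for CR is "Negative immunofixation of serum and urine". sCR is CR plus further conditions, so it inherits this one. Section 11.2 (Table 11.2, footnote 1) says that immunofixation of serum and urine, with other tests, "are required to document CR regardless of registration values".

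Section 1.3 describes the study drug: "Daratumumab is an immunoglobulin G1 kappa (IgG1k) human monoclonal antibody (mAb". Section 15.14 gives mean troughs after eight weekly doses of 593 µg/mL (subcutaneous) and 522 µg/mL (intravenous), and says that the "elimination half-life associated with linear clearance is 20 days (22"; the 22 is a coefficient of variation in percent.

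Four footnotes to Table 11.5 bear on the point:

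- Footnote a: "All response categories require two consecutive assessments (sCR, CR, VGPR, PR, MR, PD".
- Footnote b, for a patient already in CR at registration: "the patient will be considered a continued complete response if they continue to meet the complete response criteria at the next assessment". It also says that a positive immunofixation does not by itself make progression.
- Footnote c, attached to the immunofixation condition: unless several spikes are measurable at baseline, only the measurable spike is followed for response.
- Footnote k, attached to flow MRD negativity: "Requires a complete response as defined in the table".

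Section 16.411 sets no CR condition: "MRD negative response after ASCT is defined as achievement of MRD negative status in the bone marrow by flow cytometry (MPF" at the Day 100 visit. Section 16.42 defines the pre-transplant and one-year MRD rates in the same way, from marrow flow alone.

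No section mentions interference of daratumumab with electrophoresis or immunofixation, an assay to separate the two, or a rule for a new IgG kappa band.

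**The concern.** Immunofixation shows a monoclonal immunoglobulin; it does not say whether the source is the myeloma or the infusion. The study drug belongs to the class of molecule that the test looks for, and it circulates at several scheduled response assessments. A patient whose disease meets every CR condition may therefore still show a band.

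Patients who enter in CR (a category in Section 12.1) are exposed early. Section 4.1 schedules the first on-treatment immunofixation at Cycle 2 Day 1, after four weekly doses, and footnote b keeps their CR only if the criteria are still met at the next assessment.

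At stake are CR and sCR as depth of response, and the exploratory correlations with response category in Sections 16.433 and 16.434. If footnote k governs, the MRD rates after pre-transplant consolidation (objective 2.23) and after one year of maintenance (objective 2.21) are also at stake. The error runs one way, towards fewer CRs, and follows drug exposure, so it differs between visits. With no written rule, each band would be judged case by case in an open-label, single-arm trial.

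**Working it through.** **The plan's own figures.** The plan gives none for this point. Its design table (Section 16.32) concerns the Day 100 MRD rate. The exact two-stage sum, over x = 10 to 20, of P(X₁ = x | 20, p) × P(X₂ ≥ 25 − x | 25, p) gives 0.0903 at p = 0.45 and 0.9001 at p = 0.65. These match the stated 0.09 and 0.90. They need no change if MRD negativity is marrow flow alone, as Section 16 defines it.

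**Inputs for the drug level.** Trough 593 µg/mL (subcutaneous) or 522 µg/mL (intravenous), taken as 7 days after dose 8; half-life 20 days (Section 15.14). Last dose of the two-cycle schedule on Cycle 2 Day 22 (Section 7.11). Transplant 0 to 56 days after Day 28, and the Day 100 visit 90 to 110 days after transplant (Section 7.12). Maintenance dosing once per 28 days (Section 7.13).

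**Formula.** Level at g days after the last dose = trough × 2^(−(g − 7)/20).

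**Pre-transplant.** g runs from 28 − 22 = 6 days to 6 + 56 = 62 days.
- Subcutaneous: 593 × 2^(1/20) = 614; 593 × 2^(−55/20) = 88 µg/mL.
- Intravenous: 540 and 78 µg/mL.

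This covers the two-cycle schedule only. Optional cycles 3 and 4 are dosed every two weeks, so the weekly trough is not their starting point.

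**End of a 28-day maintenance cycle.** Let w = 2^(−7/20) = 0.785. The contribution of one dose is 593 ÷ [w(1 − w⁸)/(1 − w)] = 593 ÷ 3.12 = 190 µg/mL. With m = 2^(−28/20) = 0.379:
- after one dose, 190 × 0.379 = 72 µg/mL, ignoring residual drug;
- at steady state, 190 × 0.379/0.621 = 116 µg/mL.

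With the half-life moved by one CV (15.6 to 24.4 days), these become 68 to 74 and 95 to 135 µg/mL.

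**Day 100.** g runs from 6 + 0 + 90 = 96 days to 6 + 56 + 110 = 172 days, or 4.8 to 8.6 half-lives. Subcutaneous: 593 × 2^(−89/20) = 27; 593 × 2^(−165/20) = 1.9 µg/mL. With a half-life of 24.4 days the upper figure is 47. Section 15.14 also describes faster, target-mediated clearance at low doses, so these late values are more likely too high than too low.

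**Confirmation.** A CR first seen at Day 100 needs a second consecutive assessment (footnote a). Maintenance starts within 14 days of that visit, so the confirming immunofixation may fall on drug.

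**Overall response and progression.** 614 µg/mL is 0.061 g/dL. Progression on serum M-protein needs an absolute rise of at least 0.5 g/dL, and footnote b rules out progression on immunofixation alone. A CR read down to VGPR still counts in the overall response rate (Section 16.42).

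**MRD.** Under Section 16 the band has no effect. Under footnote k, suppose that every flow-negative patient would otherwise be in CR, that a share s of them have an IgG kappa M-protein, and that the drug is detected with probability f. The counted rate is then the true rate × (1 − s × f). The documents give neither s nor f.

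**The case against.** The strongest reply is that no listed primary or secondary endpoint changes because of immunofixation alone. CR rate is not an objective, overall response and progression are protected, and treatment continues alike for CR, VGPR, PR or SD (Section 13.1). The MRD consequence needs footnote k, and Section 16 omits that condition. This stands, and it limits the reach of the point.

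A second reply is footnote c. If only the measurable baseline spike is followed, a band of another isotype can be disregarded. That is a reasonable reading, and it would narrow the problem to IgG kappa patients. But the footnote speaks of spikes and does not say that it overrides a positive immunofixation. It also cannot separate the drug from an IgG kappa myeloma protein.

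Third, the documents give no detection limit. That a band appears at 70 to 120 µg/mL, or at any other level computed here, is inferred from what the drug is and what the test detects. This too stands: it leaves the size open but not the missing rule.

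**Conclusion.** The point holds in a limited form. Applied as written, the CR rule can deny or cancel CR and sCR because of the study drug. Exposure is highest before transplant, moderate in maintenance and lowest at Day 100, and the patients mainly at risk are those with an IgG kappa M-protein. MRD negativity for objectives 2.21 and 2.23 is touched only if footnote k governs; footnote k and Section 16 disagree and must be reconciled.

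The size is unknown. It ranges from nothing (no band detected) to loss of CR in every IgG kappa patient who would otherwise have it on drug. The levels assume first-order decay on the linear half-life from mean troughs; the standard deviation of the subcutaneous trough is 306 µg/mL, so individual levels vary widely.

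Three stronger readings are tempting, and the documents do not support them:

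- A reader might put a percentage on the MRD negatives lost at one year. That needs an IgG kappa share and an assumption of full detection at maintenance levels; neither is in the documents.
- A reader might infer that the Day 100 go/no-go decision loses power. Section 16 attaches no CR condition to that endpoint, and Day 100 is the least exposed visit. Any effect would need footnote k to govern, and it would lower the success count, so it would not raise the type I error.
- A reader might infer that every treated patient loses CR. Footnote c arguably excuses other isotypes, and detection is not established.

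**What to change.** Add a footnote to Table 11.5 with two rules that apply after the first daratumumab dose:

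1. If the baseline M-protein is not IgG kappa, an IgG kappa band does not count against CR.
2. If the baseline M-protein is IgG kappa and no drug-specific immunofixation result is available, record the assessment as *CR indeterminate, possible drug band*. Report CR, and any MRD rate conditioned on CR, both ways: indeterminate counted as CR and as not CR.

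The Day 100 sample should not be used to settle a band seen before transplant or during maintenance. It follows the transplant, when the disease may have changed, and daratumumab restarts within 14 days of that visit.

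State in Section 16 whether MRD negativity requires CR, and make footnote k agree.

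The cost is one footnote, one CRF field and a few patients carried as indeterminate. Rule 1 would also disregard a genuinely new IgG kappa clone for CR, although the progression criteria would still apply. No sample, visit or treatment changes.
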